4.12.4 Subject NAb Status

The subject ADA status of a subject who has one or more “NAb-positive” sample ADA statuses as defined in 4.12.2 will be defined as “NAb-positive”.

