4.12.2 Sample Anti-Mogamulizumab Neutralizing Antibody (NAb) Status

For a given sample, the anti-mogamulizumab neutralizing antibody (NAb) status will be determined using the NAb assay result as follows.

- NAb-positive: The sample is positive in the NAb assay.
- NAb-negative: The sample is negative in the NAb assay.

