4.12.3 Subject ADA Status

Each subject will be assigned a “subject ADA status” at baseline and at each subsequent time point during mogamulizumab administration.

A subject whose baseline (before administration of mogamulizumab) sample ADA status is ADA-positive will be classified as “Baseline-positive”.

During mogamulizumab administration, a subject ADA status will be determined as follows:

- ADA-positive: The subject’s samples meet either of the following criteria.
 - Treatment-induced ADA: The assay result of the sample before administration of KW-0761 is negative and one or more assay results of the samples after administration of mogamulizumab are positive.
 - Treatment-boosted ADA: The assay result of the sample before administration of mogamulizumab is positive and one or more titer values of the samples

after administration of mogamulizumab are ≥ 16 -fold of the titer value in the sample before administration of mogamulizumab.

- ADA-negative: Subject ADA status is not defined as “ADA-positive” at any time point and the sample ADA status at the last time point is not “ADA-inconclusive”.
- ADA-inconclusive: Subject ADA status is not defined as “ADA-positive” at any time point and the sample ADA status at the last time point is “ADA-inconclusive”.

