4.12.5 Determination of Anti-Mogamulizumab Antibody Incidence

The ADA analysis set for mogamulizumab will include all subjects that have both a baseline subject ADA status and at least one on-treatment subject ADA status.

The following percentage will be determined using baseline samples:

- Pre-existing ADA incidence: The number of the subjects whose ADA status is “Baseline-positive” (as defined in 4.12.3) as a percentage of the total number of subjects in the ADA Analysis Set.

The following percentages will be determined using on-treatment samples:

- Overall ADA incidence: The number of subjects whose subject ADA status is “ADA-positive” (as defined in 4.12.3) as a percentage of the total number of subjects in the ADA Analysis Set.
- Treatment-induced ADA incidence: The number of subjects who have “Treatment-induced ADA” (as defined in 4.12.3) as a percentage of the number of subjects whose sample ADA status before administration of mogamulizumab is “ADA-negative” (as defined in 4.12.3).
- Treatment-boosted ADA incidence: The number of the subjects who have “Treatment-boosted ADA” (as defined in 4.12.3) as a percentage of the number of subjects whose subject ADA status is “Baseline-positive” (as defined in 4.12.3).
- Neutralizing ADA incidence: The number of subjects whose subject ADA status is “NAb-positive” (as defined in 4.12.3) as a percentage the number of subjects in the ADA Analysis Set.

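### Neutralizing ADA incidence (SAP 4.12.4 and 4.12.5) can count subjects who are not ADA-positive under SAP 4.12.3, so it is not a subset of overall ADA incidence

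*SAP*

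**What the plan says.** SAP 4.12.2 classifies samples by the neutralizing assay alone: "NAb-positive: The sample is positive in the NAb assay".

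SAP 4.12.3 gives two routes to a subject status of ADA-positive. The treatment-induced route needs a negative pre-dose sample, after which "one or more assay results of the samples after administration of mogamulizumab are positive". The boosted route reads "Treatment-boosted ADA: The assay result of the sample before administration of mogamulizumab is positive and one or more titer values of the samples" and goes on to require a post-dose titer at least 16 times the pre-dose titer. A subject who meets neither route is ADA-negative, or ADA-inconclusive if the last sample is inconclusive.

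SAP 4.12.4 carries the heading "4.12.4 Subject NAb Status". Its one sentence begins "The subject ADA status of a subject who has one or more" NAb-positive "sample ADA statuses as defined in 4.12.2 will be defined as" NAb-positive, so the label is assigned to that same subject ADA status. It sets no baseline, timing or titer condition.

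SAP 4.12.5 limits the incidences to on-treatment samples (apart from the pre-existing one) and then defines "Overall ADA incidence: The number of subjects whose subject ADA status is" ADA-positive, and "Neutralizing ADA incidence: The number of subjects whose subject ADA status is" NAb-positive. Both are percentages of the ADA Analysis Set. For the meaning of NAb-positive it points to 4.12.3, which does not define the term; 4.12.4 does.

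**The concern.** Table 14.5.2.1 sets the neutralizing percentage beside the other ADA incidences on a common N. A reader will naturally take it as the share of subjects whose treatment-emergent antibody neutralizes. The rules do not deliver that. The ADA side has a treatment-emergence test and the NAb side has none, so the neutralizing numerator can contain subjects missing from the overall numerator.

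Two programmers could also report different neutralizing incidences from the same samples, depending on whether they add the missing link to 4.12.3. At stake is the description of immunogenicity under exploratory objective 2.

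**Working it through.** The documents give no expected ADA or NAb incidence, so there is no figure to reproduce. The check applies the rules and then shows the size with assumed counts.

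**Step 1. One subject, four rules.** Take a subject who is ADA-positive before dosing, has a titer rise below 16-fold, and has a NAb-positive sample on treatment.

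| Rule | Condition | Met? |
|---|---|---|
| 4.12.3, treatment-induced | pre-dose negative, at least one post-dose positive | No, pre-dose is positive |
| 4.12.3, boosted | pre-dose positive, post-dose titer at least 16-fold | No, rise is smaller |
| 4.12.4, NAb-positive | at least one NAb-positive sample | Yes |
| 4.12.5, neutralizing incidence | NAb-positive, on-treatment samples | Yes |

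The subject is outside the overall numerator and inside the neutralizing one.

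**Step 2. All profiles.** Assume that NAb can be positive only in an ADA-positive sample. Baseline-negative subjects then give 1 + 2 = 3 profiles. Baseline-positive subjects give 2 with no on-treatment positive and 2 × 2 × 2 = 8 with one (boosted or not, NAb at baseline or not, NAb on treatment or not). That makes 13.

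- Two are NAb-positive on treatment without being ADA-positive under 4.12.3: the Step 1 subject, with or without NAb at baseline.
- Two more are unboosted with NAb at baseline only. 4.12.4 alone would label them NAb-positive, but the on-treatment limit in 4.12.5 keeps them out of the incidence.

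**Step 3. Formulas.** Let N be the ADA Analysis Set, A the subjects ADA-positive under 4.12.3, K those among A with on-treatment NAb, and X the unboosted baseline-positive subjects with on-treatment NAb.

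- Overall incidence = A/N
- Neutralizing incidence as written = (K + X)/N
- Neutralizing incidence limited to ADA-positive subjects = K/N
- The written neutralizing figure exceeds overall when K + X > A, that is, X > A − K

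**Step 4. Assumed counts, N = 100.**

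| A | K | X | Overall | Neutralizing as written | Limited to ADA-positive |
|---|---|---|---|---|---|
| 10 | 4 | 3 | 10% | (4+3)/100 = 7% | 4% |
| 10 | 4 | 7 | 10% | (4+7)/100 = 11% | 4% |
| 5 | 2 | 4 | 5% | (2+4)/100 = 6% | 2% |
| 0 | 0 | 2 | 0% | (0+2)/100 = 2% | 0% |

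In the first row X = 3 does not exceed A − K = 6, so there is no excess, but 3 of the 7 counted subjects are not ADA-positive. In the second row X = 7 exceeds 6, and the order reverses.

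**Step 5. The other table.** Table 14.5.1.1 takes the subjects ADA-positive at the visit as the NAb denominator, and its overall row accepts any post-baseline positive without the 16-fold condition. The Step 1 subject therefore appears as ADA-positive there, but is absent from overall incidence under 4.12.5.

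**The case against.** A reader might infer a stronger fault: because 4.12.4 writes NAb-positive into the subject ADA status, that label replaces ADA-positive and neutralizing subjects drop out of overall incidence. With A = 10 and K = 4, overall would fall to (10 − 4)/100 = 6%. The wording permits this reading, but the documents do not support it:

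- The 4.12.4 heading names a NAb status, and nothing says that one label replaces the other.
- Overall incidence is anchored to ADA-positive as 4.12.3 defines it, and those criteria do not mention NAb.
- Subject labels already coexist: a boosted subject is both baseline-positive and ADA-positive, and boosted incidence uses one as denominator and the other as numerator.
- Listing 16.2.14.1.2 has separate rows for overall post-baseline ADA and for neutralizing status. Its one example is NAb-negative, so it does not show how a NAb-positive subject reads, but the layout points to two variables.

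A second objection is that no document requires neutralizing incidence to be a subset of treatment-emergent ADA. Protocol 12.6 asks for counts positive in the screening, confirmatory or neutralizing assays without a treatment-emergence condition, and any on-treatment NAb over the ADA set is a coherent descriptive measure. This stands in part: the 4% above is a recommended target, not a figure the SAP states. But the SAP does not say that it chose the broader measure, and it cites 4.12.3, the treatment-emergence section, for NAb-positive.

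It is also fair that an excess over overall incidence needs unusual data, and that Table 14.5.1.1 and the sample-level listing would let a careful reader recover the facts. The wrong cross-reference taken alone is clerical.

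**Conclusion.** The point holds in a limited form. As written, the neutralizing numerator can include subjects who are generally ADA-negative under 4.12.3 (ADA-inconclusive if their last sample is), and this does not depend on any overwriting of status. The inflation relative to a subset definition is X/N: 3 percentage points in the first illustration and 7 in the second. Neutralizing incidence exceeds overall incidence only if unboosted baseline-positive subjects with on-treatment NAb outnumber ADA-positive subjects without NAb.

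All counts are assumptions, since the documents give none, and the enumeration rests on NAb being found only in ADA-positive samples. A loss of neutralizing subjects from overall incidence is only a possible misreading of loose wording. Importance is low: immunogenicity is exploratory and descriptive, and no test or decision rule uses these percentages.

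**What to change.** In SAP 4.12.4, define subject NAb status as a variable of its own: NAb-positive if the subject is ADA-positive under 4.12.3 and has at least one NAb-positive on-treatment sample. State that subject ADA status is left unchanged. Report baseline-positive, unboosted subjects with on-treatment NAb as a separate count, so that narrowing the main figure loses no information. In 4.12.5, point the definition of NAb-positive to 4.12.4.

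The cost is a few sentences in the SAP and one extra count in Table 14.5.2.1. No new samples or assays are needed.

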4.12.5 Determination of Anti-Mogamulizumab Antibody Incidence

The ADA analysis set for mogamulizumab will include all subjects that have both a baseline subject ADA status and at least one on-treatment subject ADA status.

The following percentage will be determined using baseline samples:

- Pre-existing ADA incidence: The number of the subjects whose ADA status is “Baseline-positive” (as defined in 4.12.3) as a percentage of the total number of subjects in the ADA Analysis Set.

The following percentages will be determined using on-treatment samples:

- Overall ADA incidence: The number of subjects whose subject ADA status is “ADA-positive” (as defined in 4.12.3) as a percentage of the total number of subjects in the ADA Analysis Set.
- Treatment-induced ADA incidence: The number of subjects who have “Treatment-induced ADA” (as defined in 4.12.3) as a percentage of the number of subjects whose sample ADA status before administration of mogamulizumab is “ADA-negative” (as defined in 4.12.3).
- Treatment-boosted ADA incidence: The number of the subjects who have “Treatment-boosted ADA” (as defined in 4.12.3) as a percentage of the number of subjects whose subject ADA status is “Baseline-positive” (as defined in 4.12.3).
- Neutralizing ADA incidence: The number of subjects whose subject ADA status is “NAb-positive” (as defined in 4.12.3) as a percentage the number of subjects in the ADA Analysis Set.

4.13 Safety Analysis

The safety and tolerability of the investigational products will be determined by reported AEs, physical examinations, ECGs, vital signs, and laboratory test results.

All safety summaries will be based on the Safety Analysis Set.

4.13.1 Adverse Events

All subjects will be assessed regularly for the potential occurrence of adverse events (AEs) from the date of informed consent to 100 days after the last dose of IMP. The incidence of treatment-emergent AEs (TEAEs) will be summarized and tabulated using MedDRA (version 18.1), by System Organ Class (SOC) and Preferred Term (PT). A TEAE is defined as an AE that first occurs or worsens in severity on or after the first dose of any IMP and within 100 days after the last dose of IMP.

The National Cancer Institute Common Terminology Criteria for Adverse Events (CTCAE) (Version 4.03) will be used to grade both clinical and laboratory AEs. A subject with several occurrences of the same AE will be counted once and classified by the most severe occurrence. AEs with missing severity ratings will be classified as having unknown severity, but will be assigned Grade 3 severity for analysis and summarization.

The relationship of each AE to the IMP will be classified as related or unrelated. Any AE with an eCRF description of related will be considered related. A subject with several occurrences of the same AE will be counted once and classified as related if at least one of them is classified as related. An AE with a missing relationship to IMP will be assumed to be related to IMP for the purpose of analysis and summarization. Relationship of AEs to mogamulizumab and nivolumab will be separately recorded and analyzed.

An overview of adverse events for the Safety Analysis Set will be provided, summarizing the incidence of the following:

- Any TEAEs; Mogamulizumab-related TEAEs; Nivolumab-related TEAEs;
- Any NCI/CTCAE Grade 3/4/5 TEAEs; Mogamulizumab-related NCI/CTCAE Grade 3/4/5 TEAEs; Nivolumab-related NCI/CTCAE Grade 3/4/5 TEAEs;
- Any Treatment-emergent SAEs; Mogamulizumab-related treatment-emergent SAEs; Nivolumab-related treatment-emergent SAEs;
- Any discontinuation of study drug due to TEAEs; discontinuation of Mogamulizumab due to Mogamulizumab-related TEAEs; discontinuation of Nivolumab due to Nivolumab-related TEAEs;
- Any NCI/CTCAE Grade 5 TEAEs; Mogamulizumab-related NCI/CTCAE Grade 5 TEAEs; Nivolumab-related NCI/CTCAE Grade 5 TEAEs;

The number and percentage of subjects with TEAEs will be summarized by SOC and PT for Cycle 1 and for all cycles. A TEAE for Cycle 1 is defined as any event new or worsening prior to the Cycle 2 start date. Mogamulizumab-related TEAEs, nivolumab-related TEAEs, any IMP-related TEAEs, \geq Grade 3 TEAEs, mogamulizumab-related \geq Grade 3 TEAEs, nivolumab-related \geq Grade 3 TEAEs, any IMP-related \geq Grade 3 TEAEs, TEAEs leading to discontinuation of any IMP, any IMP-related TEAEs leading to any IMP-discontinuation, TEAEs leading to discontinuation of mogamulizumab, mogamulizumab-related TEAEs leading to discontinuation of mogamulizumab, TEAEs leading to discontinuation of nivolumab, nivolumab-related TEAEs leading to discontinuation of nivolumab, treatment-emergent SAEs, mogamulizumab-related treatment-emergent SAEs, nivolumab-related treatment-emergent SAEs, any IMP-related treatment-emergent SAEs, and fatal TEAEs will be summarized in the same manner. For these summaries, subjects with multiple AEs will be counted only once per SOC and PT.

In addition, summaries will be provided for the number and percentage of subjects with TEAEs, mogamulizumab-related TEAEs, nivolumab-related TEAEs, any IMP-related TEAEs by SOC and preferred term and by the highest NCI CTCAE grade. For these summaries, subjects with multiple adverse events will be counted only once by the highest NCI CTCAE grade within an SOC and preferred term.

As with any antibody, allergic reactions to dose administration are possible. Therefore, infusion-related acute reactions will be identified and summarized.

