### **8.5 Concomitant Treatments**

Any medication(s), including those taken within 30 days prior to the first dose of IMPs, throughout treatment with IMP, until the 30-day follow-up visit after the last dose of IMP or

until start of new anticancer therapy (whichever occurs first), and anytime thereafter if used to treat IMP-related SAEs will be recorded.

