**Table 9-2 Schedule of Events: Post-treatment Follow-up**

Procedure d	Referenced Section(s) of Protocol	Post Last Dose of IMPs Follow-up	
		30 Days	Day 100-110 and at Least Every 100 days Thereafter
Visit Window (Days)		± 5	
Serum Tumor Markers, as applicable	9.2.6	X a	X a
Tumor Assessment, MRI or CT	9.2.7	X a	X a
Adverse Events	10.3	X b	X b
Concomitant Medications	8.5/ 9.2.1	X c	X c
Survival Assessment, including Anticancer Therapies	6.3	X	X

a: Subjects who complete or discontinue treatment without disease progression will have tumor assessments collected at least every 12 weeks or per institutional standard of care until a new anti-cancer therapy is started, unequivocal disease progression is documented, or death.

b: AEs will be collected until 100 days after the last dose of IMP.

c: Concomitant medications usage will be collected until the 30-day follow-up visit after the last dose of IMP or until the start of new anticancer therapy (whichever occurs first), and anytime thereafter if used to treat IMP-related SAEs.

d: Procedures to be followed for subjects who are ongoing in the study (i.e., subjects who are continuing to receive study treatment or who are in safety or survival follow-up) at the time of data cutoff for completion of analyses are described in Section 9.5.

AE=adverse event; CT=computed tomography; IMP=investigational medicinal product; MRI=magnetic resonance imaging; SAE=serious adverse event.

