### **10.3.2 Adverse Event Reporting**

#### **10.3.2.1 Reporting Period**

The collection of AE information begins following the subject's written consent to participate in the study. For screen failures, SAEs should be collected and recorded only until the subject fails screening or withdraws consent to participate in the study, except for SAEs that occur outside of that window which are attributed to screening-specific procedures. All AEs with onset after signing of the ICF should be collected. Adverse events which occur prior to first administration of IMP should be identified as occurring pretreatment. No AE data should be entered on the electronic Case Report Form (eCRF) for screen failures. All AEs and SAEs with onset up to 100 days after the last dose of IMP should be reported. The Investigator should report any SAE that occurs after this period if the SAE is believed to be related to IMP or to a protocol-specific procedure. (NOTE: Upon implementation of Amendment 3, any treatment-related AEs and SAEs with onset after the last dose of IMP should be reported at the discretion of the Investigator to KKD Drug Safety Surveillance Department using the SAE form (Section [10.3.2.2.1](#)).

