4.7.4 Other Prior/Concomitant Medications

Prior and concomitant medications will be coded using the World Health Organization (WHO) Drug Dictionary (version September 2015). Prior medications include medications that were taken within 30 days prior to the first dose of IMP. Concomitant medications during the treatment period include medications that started at any time and were taken at any time after the start of IMP until 30 days after the last dose of IMP.

The number and percentage of subjects taking prior medications or concomitant medications during the treatment period will be summarized by anatomical therapeutic chemical (ATC) and preferred term (PT) for the Safety Analysis Set. If a subject takes more than one medication in the same ATC class, the subject will be counted only once within that classification. The same subject may contribute to two or more preferred terms within the same ATC classification.

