Note: Percentage is calculated using the number of subjects in the column heading as the denominator. WHO Drug Dictionary (September, 2015) was used for coding Medications that started at any time until 30 days after the last dose date, and were taken at any time after the first dose date are presented.

Programming note: First page of the table is for "All Cancer Types". Subsequent pages are for NSCLC SQ, NSCLC NSQ PD-L1 non-expressing, Ovarian, CRC, SCCHN, HCC, Pancreatic cancer types separately.

Repeat for the following:

Table 14.1.2.5.1
 Summary of Prior Cancer Therapy
 Safety Analysis Set

Table 14.1.2.5.2
 Summary of Post Treatment Cancer Therapy
 Safety Analysis Set

Table 14.1.2.6.1
 Summary of Prior Steroids and Immune Modulating Medications by Reason for Administration
 Safety Analysis Set

[Note: Use Reasons: Medical History Condition, Prophylaxis, Adverse Event]

All Cancer Types: Reason for administration = Medical History Condition

ATC Classification	Mogamulizumab x mg/kg + Nivolumab 240 mg N=xxx
Preferred Term	n (%)
Any Subjects with Prior Steroid and Immune Modulating Medication, Total	xx (xx.x)
ATC Classification 1	xx (xx.x)
Preferred Term 1	xx (xx.x)
Preferred Term 2	xx (xx.x)
Preferred Term 3	xx (xx.x)

Followed by

[All Cancer Types: Reason for administration = Prophylaxis]

[All Cancer Types: Reason for administration = Adverse Event]

Programming note: Add footnote "Medications with start dates within 30 days of the first dose date of the study treatment, and ended prior to the first dose date of the study treatment are presented."

Table 14.1.2.6.2
 Summary of Concomitant Steroids and Immune Modulating Medications by Reason for Administration
 Safety Analysis Set

[Note: Use Reasons: Medical History Condition, Prophylaxis, Adverse Event. Add footnote: Medications that started at any time until 30 days after the last dose date, and were taken at any time after the first dose date are presented.]

Table 14.1.2.6.3
 Summary of Prior Steroids and Immune Modulating Medications by Route of Administration
 Safety Analysis Set

[Note: Use Systemic Use, Topical. Defined as

Systemic = (Oral, Intravenous, Injection, Intrahepatic, Nasogastric, Intramuscular, Intrapleural, INTRAMUSCULAR, Subcutaneous, Epidural)

Topical = (Topical, Intraocular, Nasal, Respiratory, Rectal, Vaginal, Transdermal, Sublingual)

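### All-cause TEAEs are counted to 100 days after last dose with no summary that stops at new anticancer therapy, and the steroid tables stop at 30 days

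*SAP*

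**What the plan says.** **AE window.** SAP 4.13.1 counts as treatment-emergent any AE with first occurrence or worsening "on or after the first dose of any IMP and within 100 days after the last dose of IMP". This follows the protocol. Section 10.3.2.1 states that "All AEs and SAEs with onset up to 100 days after the last dose of IMP should be reported", and Table 9-2 footnote b that "AEs will be collected until 100 days after the last dose of IMP". None of these refers to new anticancer therapy.

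**Attribution.** The SAP tabulates TEAEs, Grade ≥3, serious and fatal events for all causes, and again as mogamulizumab-related, nivolumab-related and related to any IMP. An AE with no recorded relationship is treated as related, and one with no recorded severity as Grade 3.

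**Concomitant drugs.** Table 9-2 footnote c collects them "until the 30-day follow-up visit after the last dose of IMP or until the start of new anticancer therapy", whichever is first. Protocol 8.5 gives the same rule and its one exception: "until start of new anticancer therapy (whichever occurs first), and anytime thereafter if used to treat IMP-related SAEs will be recorded". SAP 4.7.4 summarises drugs that "were taken at any time after the start of IMP until 30 days after the last dose of IMP".

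**Steroid tables.** SAP Tables 14.1.2.6.2 (by reason, one reason being an adverse event) and 14.1.2.6.4 (by route) present "Medications that started at any time until 30 days after the last dose date, and were taken at any time after the first dose date".

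**The concern.** Safety and tolerability is the primary endpoint (Protocol 10.1) and the trial has no control arm, so nothing nets out toxicity that comes from other treatment. Subjects who stop at progression may well start another therapy inside 100 days. The protocol expects this: Section 9.3 places the end-of-treatment visit before such therapy, and Section 8.5 has a stopping rule tied to it. In the all-cause tables, a Grade ≥3 event caused by that later drug is indistinguishable from one that arose on the combination.

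Steroid and immunosuppressant use is the other half. Tables by reason for administration are a natural way to describe how much immune toxicity needed treatment, but they cover a much shorter period than the AEs they would be read against. A reader comparing the two would see late AEs with little recorded treatment and could not tell whether none was given or none was captured.

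**Working it through.** The plan gives no figure for this point, so there is nothing to reproduce. The check compares the windows.

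**1. Length of the mismatch**
- AE window: 100 days after last dose (SAP 4.13.1; Protocol 9.4, 10.3.2.1, Table 9-2).
- Routine drug recording: to the 30-day visit, ±5 days (Table 9-2).
- Gap: 100 − 30 = 70 days, or 70/100 = 70% of the post-treatment AE window. With the visit window it is 100 − 35 = 65 to 100 − 25 = 75 days, and longer if new therapy starts before the 30-day visit.
- This is a share of calendar time, not of missed treatments.

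**2. What falls in the gap**
- Drugs for IMP-related SAEs: recorded at any time. If started after Day 30 they are flagged in Listing 16.2.4.11 but excluded from Tables 14.1.2.6.2 and 14.1.2.6.4 by the 30-day start limit.
- Drugs newly started for non-serious AEs, or for SAEs judged unrelated: not recorded. The AE listing shows whether an event was treated, but not the drug or dose.
- Drugs started by Day 30 while recording was open: in the tables.

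**3. Which outputs can contain later drugs' toxicity**
- Exposed: the all-cause TEAE, Grade ≥3, serious and fatal tables. Progression is not reported as an AE (Protocol 10.3.1.1), which limits the effect on the fatal table.
- Filtered by investigator attribution: the IMP-related versions, apart from events with missing relationship.
- Outside the window: DLTs, which must be IMP-related with onset within 14 days of the last Cycle 1 dose (Protocol 6.1.2.1); Cycle 1 columns, which stop at the Cycle 2 start; laboratory shifts, limited to the treatment period (SAP 4.13.2). For a subject who never starts Cycle 2 the SAP names no end date, and I read that column as ending with the cycle.

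**4. Comparison with efficacy**
BOR, DOR and PFS stop or are censored at subsequent therapy, and BOR has a sensitivity version. OS does not stop.

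**5. Size of any inflation**
At the planned sizes, each subject whose only Grade ≥3 TEAE came from a later drug adds 1/17 = 5.9 points in the smallest cohort, 1/36 = 2.8 points in the largest and 1/184 = 0.5 points across Phase 2. The documents do not say how many such subjects to expect.

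Purely as an illustration, let g be the share with an earlier Grade ≥3 TEAE, f the share starting new therapy within 100 days, and q the share of those with a first Grade ≥3 event caused by it. The increase is (1 − g) × f × q.
- Assumed low: g = 50%, f = 20%, q = 10% gives 0.50 × 0.20 × 0.10 = 1 point.
- Assumed high: g = 30%, f = 60%, q = 50% gives 0.70 × 0.60 × 0.50 = 21 points.

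A range this wide shows only that the size is unknown.

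**The case against.** The best defence is that counting everything to Day 100 is the conservative choice for safety, and the SAP applies the protocol's own window consistently. Protocol 8.5.3 gives nivolumab a half-life of up to 25 days, so Day 100 is 100/25 = 4 half-lives. On that half-life 0.5^(30/25) = 44% remains at Day 30 and 0.5^4 = 6% at Day 100. A second drug is therefore often started while the first is still present. Ending the TEAE window there, with only events judged related kept afterwards, would make TEAE status depend on open-label attribution when attribution is hardest. It could also end the window for a subject who simply continues nivolumab: the BOR definition does not count that as new therapy, while Protocol 9.4 records later nivolumab as a new treatment. This stands as an argument against replacing the definition. It does not argue against a supplementary summary.

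It is also fair to say that the attribution tables already address IMP toxicity. They do so largely, but the all-cause tables remain planned outputs, and the missing-relationship and missing-severity rules push incomplete late records into the related and Grade ≥3 counts.

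A reader might infer that the whole primary safety result is contaminated, or that treatment of late immune events is missed outright. The documents support neither: only the all-cause outputs are exposed, and drugs for IMP-related SAEs are recorded without a time limit. Nor do they give a reason for choosing 100 days, so one cannot say that the drug-recording rule defeats its purpose.

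**Conclusion.** The point holds in a limited form. The all-cause TEAE, Grade ≥3, serious and fatal tables run through new anticancer therapy with no cut-off, flag or sensitivity summary. The steroid and immune-modulating tables omit late treatment of related SAEs that the trial does collect, and newly started treatment of non-serious late AEs is not recorded at all.

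The 65 to 75 day mismatch follows from the documents. The amount by which TEAE rates are raised does not: it depends on how many subjects start new therapy within 100 days and what happens to them, and neither rate is given. A definite percentage-point figure would be a guess, and the illustrative range should not be cited as an estimate. This is a problem of interpretability that can be put right, because dates of new therapy are recorded. It does not show that the primary analysis is wrong.

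**What to change.** **1. SAP 4.13.1.** Keep the 100-day definition as primary. Add a pre-specified supplementary summary of TEAEs, Grade ≥3, serious and fatal events censored at the start of subsequent anticancer therapy, and flag events in the listings with onset after that date. State whether continued nivolumab counts as new therapy, consistent with the BOR definition. Start dates are already in Listing 16.2.4.9. That listing imputes a missing day as the 15th but leaves year-only dates alone, so the summary needs a rule for those. The cost is a date comparison and a few extra tables.

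**2. Steroid and immune-modulating drugs.** Extend SAP Tables 14.1.2.6.2 and 14.1.2.6.4 to Day 100. For late drugs already collected for related SAEs this needs no new data. For subjects still under data capture, amend Protocol 8.5 and Table 9-2 footnote c so that systemic corticosteroids and immunosuppressants given for any AE are recorded through Day 100. The Day 100–110 visit already exists, so the cost is a little data entry.

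The limit is that Section 9.5 ends data entry for all subjects on the sponsor's notification, so the recording change helps only until then. The table changes can be made at any time before database lock.
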